Study sites will be Mental Health NHS Trusts with MHDU, defined broadly as a hospital-based unit that receives targeted referrals of people in acute mental health crisis, prior to a decision about admission being made, for purposes of assessment, therapeutic input, and either subsequent admission, discharge or forward signposting to appropriate recovery and preventative services. To maximize generalisability, MHDUs in four contrasting Mental Health NHS Trusts will be evaluated in depth; South West London & St George's, Lincolnshire, Sheffield and Birmingham.

Sites have been chosen for reasons of a) feasibility; we have the support of host NHS Trusts to access participants and data, and b) there is an appropriate level of variation (as identified in the WP1 mapping exercise) in configuration of the MHDU model across the four sites to allow comparison and ascertain models of MHDU which are likely to be optimal with respect to service productivity, quality of care as experienced by service users and cost-benefit.

Primary and secondary outcome measures

ITS will be used to identify any effects observed across the four participating MHDUs on a range of outcome measures focussed on the activities of the relevant acute and mental health Trusts. The primary outcome measures (for mental health Trust and A&E department – acute Trust – respectively) are changes in the number and pattern of:

- informal admissions to mental health Trust adult inpatient wards
- A&E psychiatric presentations

The secondary outcomes are changes in:

Mental health Trust

- total inpatient admissions
- number of 0-5 day inpatient admissions
- average length of inpatient stay (bed days)
- compulsory admissions
- occupied bed days (daily mean for the week)
- out of area admissions (from the site MH Trust to other MH Trust or private provider)
- number of psychiatric liaison episodes in A&E
- transfer to MDHU by ambulance and police

Acute Trust (collected for each hospital which refers to the site MDHU)

- number of 4 hour psychiatric A&E breaches
- average length of psychiatric A&E wait
- number of 12 hour trolley waits
- number of admissions to an acute bed
- arrival at A&E by ambulance and police

Data collection for ITS

Outcome data will be collated as weekly series for 24 months pre- and 24 months post-implementation of MHDUs, totalling 208 (weekly) time points. This is more than the 40 data points (20 pre- and 20 post-

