Formal statistical analysis will include a time series regression analysis, used to estimate the effectiveness of introducing MHDUs on outcome variables. We will adopt an autoregressive integrated moving average (ARIMA) modelling approach,⁴³ as it allows for accurate analysis of outcomes, taking into account any serial correlation, background variation and underlying trends independent of the intervention over time. ARIMA modelling has previously demonstrated successful prediction emergency department (ED) presentations and hospital admission,⁴⁴ including psychiatric visits.⁴⁵

Initially, for each outcome, to check for serial auto-correlation due to repeated measures, we will examine the plot of residuals from regression analyses and use the Durbin-Watson test. Where no significant autocorrelation is detected, we will use a simple time series regression model. If significant autocorrelation exists, then adjustment for autocorrelation will be made using the ARIMA method.

For each outcome, we will calculate regression coefficients corresponding to both change in level (outcome) and trend (slope) after the introduction of MHDUs. In this model, the estimated parameters of interest are as follows: 1 the underlying trend prior to MHDU introduction (b1); 2 the level change immediately following MHDU introduction (b2); 3 the slope change from pre- to post-MHDU introduction

(using the interaction between time and change; b3); 4 the trend (slope change) following MHDU introduction (b1_b3).

Secondary analyses will include separate time series analyses of informal admissions to mental health Trust adult inpatient wards administered considering only people with discharge from psychiatric inpatient services in the last 24 months. In a similar manner, separate analyses of A&E psychiatric presentations will be administered considering only people with a previous A&E visit in the last 24 months. This is to ensure that we can estimate the effect of introducing MDHU on those populations most likely to be repeat users of mental health inpatient care and A&E respectively. External validity will be explored by examination of primary outcomes in subgroups, including but not limited to gender and ethnicity.

Semi-structured interviews; Data collection and interpretation of time series analysis

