As in WP2, MHDUs in four contrasting Mental Health NHS Trusts will be evaluated in depth; South West London & St George's, Lincolnshire, Birmingham and Sheffield. Sites have been chosen for reasons of a) feasibility; we have the support of host NHS Trusts to access participants and data, and b) there is an appropriate level of variation in configuration of the MHDU model across the four sites (see Table 1 above) to allow comparison and ascertain models of MHDU which are likely to be optimal with respect to service productivity, quality of care as experienced by service users and cost-benefit. The counterfactual (control) will be constructed from selected sites without a MHDU, as identified in WP1.

Outcome measures

The synthetic control approach will be used to compare effects observed across the four participating MHDUs against selected control sites (identified from the service mapping exercise; WP1) on outcome measures focussed on the activities of the relevant acute and mental health Trusts. The primary outcome measures (for mental health Trust and A&E department – acute Trust – respectively) are changes in the number and pattern of:

- Informal admissions to mental health Trust adult inpatient wards
- A&E psychiatric presentations

In addition, where data can be accessed using NHS Digital Hospital Episodes Statistics and the Mental Health Services Data Set (see below), secondary outcomes of interest will be changes in the numbers and patterns of:

Mental health Trust

- total inpatient admissions
- number of 0-5 day inpatient admissions
- average length of inpatient stay (bed days)
- compulsory admissions
- occupied bed days (daily mean for the week)
- out of area admissions (from the site MH Trust to other MH Trust or private provider)
- number of psychiatric liaison episodes in A&E
- transfer to MDHU by ambulance and police

Acute Trust (collected for each hospital which refers to the site MDHU)

- number of 4 hour psychiatric A&E breaches
- average length of psychiatric A&E wait
- number of 12 hour trolley waits
- number of admissions to an acute bed
- arrival at A&E by ambulance and police

Data collection for synthetic control study

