Outcome data will be collated at treated and control unit sites as monthly series for 24 months pre- and 24 months post-implementation of MHDUs), totalling 49 time points. This provides us more than the 40 data points (20 pre- and 20 post-change) typically considered as adequate for valid ITS model analysis,⁴⁰ and provides sufficient power to detect medium effects where they exist.

As with ITS (WP2), the metrics used as dependent measures within the synthetic control study will include key parameters associated with acute and psychiatric hospital activity. Aggregated service use data over the relevant 48 months for treated and untreated units will be sourced from Hospital Episodes Statistics (HES) and the Mental Health Services Data Set (MHSDS). HES and MHSDS are databases recording all admissions, outpatient appointments and A&E attendances at NHS hospitals in England and Mental Health NHS Trust service use respectively (see http://content.digital.nhs.uk/ for details).

Where there is more than one A&E department referring to the MDHU or control (counterfactual) in any one site, we will aim to collect A&E data from each acute hospital Trust, and at least from the main general hospital in that area. Research costs are included in the proposed funding to enable timely access to HES and MHSDS.

Analytical strategy

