Difference-in-Difference (DID) is often used to estimate the impact of an intervention when data exists before and after a policy change. DID relies on the assumption that, in the absence of the intervention, the expected outcomes for the treated and control units would have followed parallel trends. However, this assumption is often implausible, particularly in a health policy setting where unobserved covariates may differ over time between the comparison groups. When the parallel trends assumption fails, DID may provide biased estimates.^{46, 47} The original Synthetic Control (OSC) method introduced by Abadie et al.^{48, 49} offers an alternative to DID, which avoids the parallel trends assumption and allow for the effects of unobserved covariates to vary over time. The central idea of OSC is to construct a weighted combination of untreated units to represent a counterfactual treatment free outcome for the treated region. Weights are chosen so that the treated region and the synthetic control region have similar values of the outcome and covariates over the pre-intervention period. However, the OSC approach has been shown to provide biased estimates under certain circumstances: when the treated units lie outside the convex hull of the controls;⁵⁰ when there are too few pre-intervention time periods⁵¹ or when there are endogenous treatment effects.⁵² Further, the OSC estimator is not designed for high dimensional data or multiple treated units, does not allow for heterogenous effects and offers uncertainty estimates that are cumbersome and not easily interpretable.⁵³

Recent methodological advances include Micro Synthetic Control (MSC)⁵⁴, which allows for high dimensional data, and Generalised Synthetic Control (GSC)⁵³, which combines insights from interactive fixed effect modelling with insights from the OSC method. These methods overcome the limitations of DID and OSC, providing more reliable estimates in scenarios where there are no parallel trends or few pre-intervention periods. In general, GSC is favourable, however MSC offers more reliable estimates when there is strong serial dependence of the error terms.⁵⁵ If no strong serial correlation is detected in the outcome of interest, analysis will be performed using GSC, otherwise MSC.

WP4.Quantitative longitudinal study using electronic patient record (months 4-21)

Objective

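### Ambulance and police transfers to the MHDU are listed as an effect outcome in WP2 and WP3, but are zero by construction before opening and at control sites, so the estimate only restates unit activity

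*Protocol*

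**What the plan says.** In Protocol Section 5, WP2 (Primary and secondary outcome measures), the purpose is stated as: "ITS will be used to identify any effects observed across the four participating MHDUs on a range of outcome measures". The secondary list for the mental health Trust includes "transfer to MDHU by ambulance and police" (the protocol uses MDHU and MHDU for the same unit). The observation window is "24 months pre- and 24 months post-implementation of MHDUs, totalling 208 (weekly) time points". The WP2 analytical strategy then says "For each outcome, we will calculate regression coefficients corresponding to both change in level (outcome) and trend (slope) after the introduction of MHDUs", and exempts no outcome.

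WP3 (Outcome measures) repeats the item in its secondary list, on the condition that the data can be obtained from Hospital Episodes Statistics (HES) or the Mental Health Services Data Set (MHSDS). Its comparison is defined by "The counterfactual (control) will be constructed from selected sites without a MHDU", and its data by "Outcome data will be collated at treated and control unit sites as monthly series for 24 months pre- and 24 months post-implementation". In describing the original synthetic control method, the WP3 analytical strategy explains that "Weights are chosen so that the treated region and the synthetic control region have similar values of the outcome and covariates over the pre-intervention period". The analysis itself is to use the generalised version or, if serial correlation is strong, the micro version.

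Both lists also contain, under the acute Trust, A&E arrivals by ambulance and police. WP4 (Data collection) collects transfers to the MHDU for each participant over 9 months before admission and 9 months after discharge. Its participants are people at their first MHDU referral or admission.

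**The concern.** Both designs estimate an effect by comparing what happened after opening with what would have happened without the unit. For this outcome the second quantity is known in advance: without a unit there are no transfers to it. The comparison adds nothing to the post-opening count.

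The risk is one of interpretation. A table of time series coefficients would show a rise in ambulance and police transfers after MHDU introduction, probably with a small p-value, beside outcomes for which such a coefficient does carry information. A reader could take it as evidence that the unit increased ambulance or police activity. WP6 also draws on changes in secondary outcomes from WP2 and WP3 for costing. The count of transfers is a legitimate activity figure there, but not as an estimated effect on conveyance.

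**Working it through.** **Inputs.** Weekly points in WP2: 208, half before opening, so 208 / 2 = 104 pre-opening weeks. WP3: 24 + 24 = 48 months per unit. Secondary outcomes: 8 mental health Trust + 5 acute Trust = 13 in each work package. The protocol gives no transfer volume, so weekly means of 0.25, 0.5, 1 and 3 are assumed as a range.

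**The plan's own figure.** The only power statement for WP2 is above 99% at 208 points for a medium effect, with one parameter tested and up to five factors. With f² = 0.15 (assumed conventional medium effect) and two-sided alpha 0.05 (stated in WP4, assumed here), the noncentrality is 0.15 × 208 = 31.2 and the error degrees of freedom are 208 − 5 − 1 = 202. The noncentral F distribution then gives power 0.9998. The figure reproduces, and the present point does not depend on it.

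**WP2 model.** With t the week, T the opening week and I = 1 from T onwards:

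y(t) = b0 + b1·t + b2·I + b3·I·(t − T)

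Each segment has its own level and slope, so the two halves are fitted separately.
- Before opening, y(t) = 0 in all 104 weeks, so b0 = 0 and b1 = 0 exactly.
- After opening, b2 is the fitted transfer level at opening and b3 the slope of transfers since opening. The post-opening trend is b1 + b3 = b3.
- Hence b2 and b3 describe post-opening activity only. If the series is flat, b2 equals the mean weekly number of transfers.

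**Simulation of that model.** 1,000 runs per row: 104 zeros followed by 104 flat Poisson counts, ordinary least squares, joint test of b2 and b3 at 0.05. Nothing changes except that the unit exists.

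| Assumed transfers per week | Mean b2 | Mean b3 | Runs with p < 0.05 |
|---|---|---|---|
| 0.25 | 0.25 | about 0 | 54% |
| 0.5 | 0.50 | about 0 | 97% |
| 1 | 1.01 | about 0 | 100% |
| 3 | 2.98 | about 0 | 100% |

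**WP3 model.** The treated unit is zero in its 24 pre-opening months and each control is zero in all 48.
- Weighting: for any weights w(j), the synthetic control is Σ w(j) × 0 = 0. Every choice of weights gives zero pre-opening error on this outcome. Covariates could still select weights, but the weighted outcome remains 0.
- Factor model (the generalised version): the control outcome matrix is all zeros and has rank 0, so no factor can be estimated from it.
- Estimated effect: y(t) − 0 = y(t), the raw transfer count.

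**WP4.** Participants enter at their first MHDU referral or admission, so transfers to the MHDU in the preceding 9 months are essentially zero by eligibility. A before-after difference would again restate post-discharge use.

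**The case against.** The strongest reply is that the consequences are small.

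- **Secondary status.** This is one of 13 secondary outcomes, and the WP2 and WP3 objectives concern inpatient admissions and A&E episodes. That stands.
- **WP3 is conditional.** The item applies only if HES or MHSDS record it, which the protocol does not claim, and the WP3 design text speaks of impact on primary outcome variables. The item may never be analysed there. But the condition concerns data access, does not exclude the item, and has no counterpart in WP2.
- **Visibility.** WP2 plans graphs, in which an all-zero pre-period would be obvious. That reduces the risk of misreading without giving the coefficient a meaning.
- **Conveyance is already covered.** A&E arrivals by ambulance and police exist before opening and at controls. This stands, and is a reason to drop the faulty item.
- **The slope has content.** b3 does show whether use grew after opening. That is description, with no informative counterfactual.

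A reader might also infer more than the documents support. First, that WP2 must return a significant increase: at 0.25 transfers per week only 54% of simulated runs did, and the protocol gives no volume. Second, that the synthetic control model cannot be fitted at all: a weighted estimate can be computed but is uninformative, and the failure to estimate factors concerns the generalised version. Third, that acute-hospital data collection is undefined at control sites because the outcome list refers only to hospitals referring to the MHDU: WP3 (Data collection) extends collection to controls and requires at least the area's main general hospital.

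**Conclusion.** The point holds as wrong as written, at modest weight. The protocol places the item among its effect outcomes and applies the level and slope model to every outcome, although this one is zero by construction in all 104 pre-opening weeks and in every month at every control. The WP2 coefficients describe unit activity after opening, and the WP3 effect is the raw transfer count. Neither says whether ambulance or police conveyance changed.

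The extent is one of 13 secondary outcomes in each of two work packages, conditional on data access in WP3, with the primary outcomes unaffected. The structural argument needs no assumption beyond the outcome's own wording and the absence of a unit before opening and at controls. Only the significance percentages rest on assumed volumes, flat Poisson counts and ordinary least squares.

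**What to change.** 1. Remove the item from the WP2 and WP3 effect-outcome lists and report it descriptively after opening only, as a count or rate by site.
2. Use the already listed A&E arrivals by ambulance and police for the effect analysis.
3. If total conveyance is of interest, define a measure that exists before opening and at controls and counts each crisis episode once, excluding A&E-to-MHDU transfers. Simply adding A&E arrivals to MHDU transfers would not do: WP5 describes paramedics and police moving people from A&E to the unit, so one such episode would count as 1 before opening and 1 + 1 = 2 after, an artificial rise.
4. In WP4, state that this item is described after discharge and not compared with the pre-admission period. The WP4 strategy makes such comparisons only where appropriate, so one sentence is enough.

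Items 1, 2 and 4 cost wording only and need no new data. Item 3 is optional and, for WP3, depends on whether HES or MHSDS hold the necessary fields.
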